# 8.4.1.15.2 Cognitive Impairment (Montreal Cognitive Assessment – MoCA)

The Montreal Cognitive Assessment (MoCA) is used as one of the exclusion criteria, and will be assessed at screening and visit 3 (day 42) or early termination.

The MoCA was developed as a tool to screen subjects who present with mild cognitive impairment. A total of 30 items are evaluated as follows: The short-term memory recall task (5 points) involves two learning trials of five nouns and delayed recall after approximately 5 minutes. Visuospatial abilities are assessed using a clock-drawing task (3 points) and a three-dimensional cube copy (1 point). Multiple aspects of executive functions are assessed using an alternation task adapted from the Trail Making B task (1 point), a phonemic fluency task (1 point), and a two-item verbal abstraction task (2 points). Attention, concentration, and working memory are evaluated using a sustained attention task (target detection using tapping; 1 point), a serial subtraction task (3 points), and digits forward and backward (1 point each). Language is assessed using a three-item confrontation naming task with low-familiarity animals (lion, camel, rhinoceros; 3 points), repetition of two syntactically complex sentences (2 points), and the aforementioned fluency task. Finally, orientation to time and place is evaluated (6 points). The

Amendment 04, Final Version 1.0 07/Nov/2018 Page 55 / 142

total possible score is 30 points; a score of 26 or above is considered normal. An MoCA sample questionnaire has been included in Appendix 18.10.

## **8.4.1.15.3** Hamilton Rating Scale for Depression (HAM-D)

The Hamilton Depression Rating Scale (HAM-D) is one of the secondary efficacy endpoints and will be assessed at screening, visit 2 (day 14), visit 3 (day 42) or early termination, and follow-up visit (28 days after the last IMP administration).

The HAM-D was designed as a way of determining a patient's level of depression before, during, and after treatment. Although the HAM-D form lists 21 items, the scoring is based on the first 17 (0-7 [normal], 8-13 [mild depression], 14-18 [moderate depression], 19-22 [severe depression], and  $\geq$ 23 [very severe depression]). For the total sum, 8 items are scored on a 5-point scale, ranging from 0 (not present) to 4 (severe), and the remaining 9 are scored from 0 to 2. Subjects with a HAM-D score  $\geq$  17 at screening will be considered as excluded from the study. Patients with elevated HAM-D during the study will be managed as per the standard of care at the site, including an assessment by the investigator of the need for further mental health evaluation.

An HAM-D sample questionnaire has been included in Appendix 18.9.

## 8.4.1.15.4 Columbia-Suicide Severity Rating Scale (C-SSRS)

The Columbia-Suicide Severity Rating Scale (C-SSRS) will be assessed at screening, visit 2 (day 14), visit 3 (day 42) or early termination, and follow-up visit (28 days after the last IMP administration).

The C-SSRS supports suicide risk assessment through a series of simple, plain-language questions that anyone can ask. The answers help users identify whether someone is at risk for suicide, assess the severity and immediacy of that risk, and gauge the level of support that the person needs. Users of the C-SSRS tool ask people whether and when they have thought about suicide (ideation), what actions they have taken (and when) to prepare for suicide, and whether and when they attempted suicide or began a suicide attempt that was either interrupted by another person or stopped of their own volition.

Columbia University, the University of Pennsylvania, and the University of Pittsburgh — supported by the National Institute of Mental Health (NIMH) — developed the screening tool for a 2007 NIMH study of treatments to decrease suicide risk among adolescents with depression. The C-SSRS, based on more than 20 years of scientific study, filled an urgent need for suicide research and prevention: a better way to uniformly and reliably identify people who are at risk. The C-SSRS achieved accurate and comparable results by using consistent, well-defined, and science-based terminology. Just as important as its ability to identify who might attempt suicide, it was the first scale to assess the full range of a person's suicidal ideation and behavior, including intensity, frequency, and changes over time.

In 2011, the Centers for Disease Control and Prevention adopted the scale's definitions for suicidal behavior and recommended the use of the C-SSRS for data collection. In 2012, the Food and Drug Administration declared the C-SSRS the standard for measuring suicidal ideation and

Protocol No.: BB-2001-201b EudraCT No.: 2017-000877-35 Amendment 04, Final Version 1.0 07/Nov/2018 Page 56 / 142

behavior in clinical trials. Today, the C-SSRS is used in clinical trials, public settings, and everyday situations, such as in schools, faith communities, hospitals, and the military, to identify who needs help — saving lives in 45 nations on six continents.

Subjects with a positive response on the C-SSRS (an answer of 'yes' to any of the 6 questions) will be considered as excluded from the study. Any positive finding on the C-SSRS during the study will be managed as per the standard of care at the site, including an assessment by the investigator of the need for further mental health evaluation.

A C-SSRS sample questionnaire has been included in Appendix 18.12.

# 8.4.1.15.5 Brief Psychiatric Rating Scale Positive Subscale (BPRS+)

The Brief Psychiatric Rating Scale Positive Subscale (BPRS+) will be assessed at screening, visit 2 (day 14), visit 3 (day 42) or early termination, and follow-up visit (28 days after the last IMP administration).

The BPRS is an instrument originally developed to characterize psychopathology and to measure change in clinical psychopharmacology research. It permits the recording of severity of 18 (originally 16) distinct signs and symptoms of psychopathology such as hostility, suspiciousness, hallucination, and grandiosity, based on clinical interview of a patient. It is particularly useful in gauging the efficacy of treatment in patients who have moderate to severe psychoses, and based on the clinician's interview with the patient and observations of the patient's behaviour over the previous 2-3 days. The patient's family can also provide the behaviour report. The rater enters a number for each symptom construct that ranges from 1 (not present) to 7 (extremely severe).

Psychiatric symptoms, associated with PD itself and specifically in patients with Parkinson's psychosis, consist primarily of paranoid delusions, visual hallucinations and/or other sensory disturbances. Psychosis in PD most commonly manifests in visual hallucinations. Auditory hallucinations occur less commonly in PD psychosis (unlike hose seen in schizophrenia) and typically co-occur with visual hallucinations. Tactile, olfactory and gustatory hallucinations have also been reported in PD psychosis and also tend to co-occur with visual hallucinations, but less commonly than other forms of hallucinations. Delusions and is organized thinking are also seen in PD psychosis, although they are not as common as visual hallucinations.

While it is assumed that in this study adverse events known to occur with Bavisant will be directly assessed along with any sleep related effects, the Brief Psychiatric Rating Scale Positive Symptoms Subscale (BPRS+) would be appropriate to observe for psychiatric symptoms occurring in this study, with this population.

The BPRS+ has been used in studies of major depressive disorders to observe for psychotic features occurring with drug treatment. It consist of 4 (Conceptual Disorganization, Suspiciousness, Hallucinatory Behaviour, and Unusual Thought Content) of the 18 domains of the full Brief Psychiatric Rating Scale and would cover those symptoms seen with Parkinson's psychosis. It could readily be taught to neurologists to perform in a reasonable amount of time during a study visit without becoming an undue burden on either the rater or the subject. The full BPRS with its 18 items would require extended time to teach and to perform without offering any clear additional benefit over the BPRS+ here.

Protocol No.: BB-2001-201b EudraCT No.: 2017-000877-35 Amendment 04, Final Version 1.0 07/Nov/2018 Page 57 / 142

Alternatives, such as the Positive and Negative Syndrome Scales (PANSS) have been discarded as being primarily used in schizophrenia which has psychotic features which differ from those seen with Parkinson's disease.

A BPRS+ sample questionnaire has been included in Appendix Error! Reference source not found.

### 8.4.1.15.6 Rater Qualification and Certification

In order to ensure satisfactory training of raters and quality execution with regards to data collection, raters assigned to this study will be required to adhere to certain requirements prior to participation in the trial. All raters will be required to successfully complete the full scope of rater training requirements prior to rating any subjects in this study. The rater training and certification process will consist of verifying rater qualification via completion of a Rater Experience Survey and completion of training or certification on key scales. Raters who successfully complete requirements will be approved for participation in the study. Raters who do not meet all the qualification and training requirements may be prohibited from participating as raters on this trial.

## 8.4.1.15.7 Maintenance of Wakefulness Test (MWT)

The Maintenance of Wakefulness Test (MWT) is one of the secondary efficacy endpoints and will be assessed at baseline (day -7 to day -2) and visit 3 (day 42) or early termination at specific sleep centres.

The MWT is an evaluation used as a quantitative polysomnographic (PSG) measurement of daytime wakefulness/somnolence during soporific circumstances. The assessment of such disorders requires a polygraphic approach in which multiple physiologic parameters are recorded. This is usually performed during the day following a night sleep with some electrodes placed on the head, around the eyes and on the chin. The test isolates subjects from outside factors that can influence their ability to fall asleep (temperature, light, noise, activity). The test consists of four sleep trials timed at 2-hourly intervals, with the first trial performed 2 to 3 hours after the normal wake time and after having eaten a light breakfast at least one hour before the first trial. During each trial, subjects will sit quietly on the bed with both back and head supported by a pillow, and subjects will be asked to look directly ahead and try to stay awake as long as they can. If they fall asleep, they will be woken up after 90 seconds and the trial will end if the subjects do not fall asleep within 40 minutes. Start and stop times for each trial, sleep latency, total sleep time, stages of sleep achieved for each trial, and the mean sleep latency (the arithmetic mean in minutes of the four trials) will be recorded, considering sleep latency as the time from lights out until the first epoch of greater than 15 sec of cumulative sleep in a 30-sec epoch of either 3 consecutive epochs of stage 1 sleep, or one epoch of any other stage of sleep. In between trials subjects must stay awake and stay out of bed. From midnight of the day before the test, drinks containing caffeine (tea, coffee, cola drinks, energy drinks, etc.) need to be avoided. In order to harmonize the practice parameters of the MWT, a Task Force of content experts was appointed by the American Academy of Sleep Medicine and their recommendations were developed by the Standards of Practice Committee and reviewed and approved by the Board of Directors of the American Academy of Sleep Medicine. A copy of these recommendations is included in Appendix 18.4.

Amendment 04, Final Version 1.0 07/Nov/2018 Page 58 / 142

## 8.4.1.15.8 Polysomnography

The Polysomnography (PSG) is one of the secondary efficacy endpoints and will be assessed at baseline (day -7 to day -2) and visit 3 (day 42) or early termination at specific sleep centres.

The PSG is a sleep study which consists of a simultaneous recording of multiple physiologic parameters related to sleep and wakefulness and is used to evaluate abnormalities of sleep and/or wakefulness and other physiologic disorders that have an impact on or are related to sleep and/or wakefulness. For a standard test, the subject will have the electroencephalogram (EEG), the electro-oculogram (EOG), the electromyogram (EMG), and the electrocardiogram (ECG) performed. The American Association of Sleep Technologies developed the technical guideline of sleep technology for a standard polysomnography, updated July 2012. A copy of this guideline is included in Appendix 18.5.

## 8.4.1.15.9 Free Living Activity

Approximately half (50%) of subjects participating in the clinical study will be offered an opportunity to take part in the assessment of free living activity as an exploratoty assessment. A wrist-worn actigraphy device (GENEActiv®) will be provided to these subjects and they will be required to wear the actigraphy device on their non-dominant wrist for 7 consecutive days during the baseline period (day -7 to day -1) and 7 consecutive days **before** the last dose on visit 3 (day 35 to day 42).

The wrist-worn actigraphy device (GENEActiv®) is a tri-axial accelerometer which provides an objective measure of physical activity levels. A study manual with instructions will be provided to both the investigators and the subjects.

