# Treatment Visit 3 (Day 42 ±3)

This visit will be performed 6 weeks after the 1st treatment administration (Day 1). The following examinations/procedures will be performed:

- Physical examination
- Vital signs
- Laboratory (haematology, biochemistry), serum pregnancy test (for women of childbearing potential)
- Electrocardiogram, heart rate, blood pressure
- Assessment of sleepiness scales: ESS, SCOPA-Sleep, PDSS-2
- Maintenance of Wakefulness Test (MWT)

Protocol No.: BB-2001-201b EudraCT No.: 2017-000877-35 Amendment 04, Final Version 1.0 07/Nov/2018 Page 61 / 142

- Polysomnography
- Cognitive assessment (MoCA)
- Columbia-Suicide Severity Rating Scale (C-SSRS)
- Fatigue assessment (FSS)
- Other scales: UPDRS Part III, HAM-D and BPRS+
- Wrist-worn actigraphy assessment 7 days continuously **before** last dose (day 35 to day 42).
- Wrist-worn actigraphy device return
- Drug return and accountability
- Recording of adverse events
- Recording of concomitant medication
- Eye examination (should be performed after the last treatment on Day 42 and before the follow up safety call)

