### 8.6.3 Dosages and Regimen

Each subject who qualifies for the study will receive wallet cards containing tablets of double-blind study medication. Subjects will receive 1 wallet card of their assigned treatment at Visit 1 (for 2 weeks treatment period) and 2 wallet cards at Visit 2 (for 4 weeks treatment period).

Subjects will be instructed to take 1 tablet orally per day at the same time in the morning, with or without food. The first dose is to be taken the day after randomisation when study medication has been dispensed to the subject.

The investigator or designee must instruct the subject to bring each of their study medication containers (wallet cards) to each clinic visit, regardless of whether the study medication cards are empty.

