10.3 Exploratory Efficacy Analysis

We aim to characterise the changes in free-living activity by means of wrist-worn actigraphy. GENEActiv accelerometers are worn on the wrist and measure tri-axial acceleration with a sample

frequency of 100Hz. The device also measures temperature and light levels. The data is collected pre- and post- dosing (V3), each over a period of seven days. We aim to measure differential physical activity behaviour, and also the length and frequency of daytime sleep episodes.

The data is to be processed using the calibrated GENEActiv tracker data pre-processing package in R. We extract 12-hour daytime records and convert the accelerometer to gravity-subtracted Signal Vector Magnitudes (SVMgs), which is our measure of instantaneous physical intensity. The time-series is downsampled (100x) to one second intervals by averaging the instantaneous SVMgs across the 100 time points. The averaged SVMgs are grouped into four intensity levels groups: Sedentary (< 4.5), Light (4.5-16.5), Moderate (16.5-42), and Vigorous (> 42). These threshold boundaries may change as thresholds used in existing studies are calibrated for different populations. The summary statistics we aim to extract are bout lengths and frequencies, where a bout is a continuous episode of physical activity at a specific intensity levels band. Using paired t-tests, we aim to demonstrate a reduction in sedentary activity and an increase in light to vigorous activity in the dosed population. Using automatic changepoint detection methods (such binary segmentation methods and its extensions, with the fused lasso total variation regulariser, together with Bayesian approaches such as Dirichlet process hidden Markov models.) for detection of sleep boundary times, we also, independently of activity level measurements, aim to quantify the frequency and lengths of daytime sleep episodes.

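### For subjects who do both assessments, the baseline free-living actigraphy week always contains the MWT day and the second week may not; SAP 10.3 excludes that day from neither

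*Protocol*

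**What the plan says.** Protocol 8.4.1.15.9 offers actigraphy to about half of the subjects. The device is worn "for 7 consecutive days during the baseline period (day -7 to day -1"), and again for seven days ending before "the last dose on visit 3 (day 35 to day 42"). The schedule of assessments (18.15, footnote 2) asks for continuous wear.

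The MWT "will be assessed at baseline (day -7 to day -2) and visit 3 (day 42) or early termination at specific sleep centres" (Protocol 8.4.1.15.7). Polysomnography has the same timing: it "is one of the secondary efficacy endpoints and will be assessed at baseline (day -7 to day -2) and visit 3 (day 42"). Section 8.4.2 gives the second visit as "Treatment Visit 3 (Day 42 ±3") and lists MWT, polysomnography, the actigraphy assessment and device return under it. Subjects "take 1 tablet orally per day at the same time in the morning" (8.6.3).

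SAP 10.3 takes 12-hour daytime records from the seven days before dosing and the seven days at Visit 3. It grades movement from sedentary to vigorous and plans paired t-tests to show less sedentary and more active time in dosed subjects. Separately, it "aim to quantify the frequency and lengths of daytime sleep episodes". Neither document removes or flags a sleep-laboratory day. A device manual is mentioned but is not part of these documents.

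**The concern.** The exploratory objective is free living activity compared with placebo. The MWT day is not free living. "The test consists of four sleep trials timed at 2-hourly intervals"; in each one the subject sits still on a bed, and between trials must stay awake and out of bed. Stillness and sleep during the trials come from the test, yet they would be scored as free-living sedentary time and daytime sleep.

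The larger difficulty is asymmetry. If the laboratory day sits in the baseline week and not in the second, a pre/post comparison sets a week with a test day against a week without one. The outcome is mainly exploratory, but Protocol 11.1.5 and SAP 10.2 also list motor function from the wrist device among the secondary analyses.

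**Working it through.** **Inputs.** Wear windows: Protocol 8.4.1.15.9. MWT days, four trials, 40-minute limit, waking after 90 seconds: 8.4.1.15.7. Visit 3 window: 8.4.2. Morning dosing: 8.6.3. The 12-hour record: SAP 10.3. Subset sizes: 8.4.1.15.9 and 18.15, footnote 11. Planned N of 230: 7.1. The documents give no MWT latencies, so those below are assumptions.

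**Baseline overlap.** Day -7 to Day -1 is 7 days, which reproduces the plan's figure. The permitted MWT days, Day -7 to -2, number 6, and all 6 lie inside the wear week.

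**Second week.** Day 35 to 42 inclusive is 42 − 35 + 1 = 8 calendar days. It is seven 24-hour periods (42 − 35) only if wear stops before the Day 42 dose. Whether the MWT day is inside depends on the reading:

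| Visit 3 on | Wear through Day 42 | Wear ends before the Day 42 morning dose |
|---|---|---|
| Day 39 to 41 | inside | inside |
| Day 42 | inside | outside |
| Day 43 to 45 | outside | outside |

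If wear instead ends before a dose taken on the morning of Visit 3 itself, the MWT day is outside whatever the visit date.

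**Amount per record.** One daytime record is 12 × 60 = 720 minutes, and a week is 7 × 720 = 5,040 minutes.

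- Maximum stillness, awake through every trial: 4 × 40 = 160 minutes. 160/720 = 22.2% of that day; 160/5,040 = 3.2% of the week.
- Maximum sleep, asleep in every trial: 4 episodes × 1.5 minutes = 6 minutes.
- The two maxima exclude each other: the first needs no sleep in any trial, the second sleep in all four.
- For a subject who sleeps in every trial, still time is 4 × (latency + 1.5). Assumed mean latencies of 5, 10, 20 and 30 minutes give 26, 46, 86 and 126 minutes, or 0.5%, 0.9%, 1.7% and 2.5% of the week.

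**Direction.**

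- MWT day in the baseline week only: stillness and episodes are added before treatment and not after, so the change from baseline leans toward less sedentary time and fewer daytime sleep episodes, in every arm.
- MWT day in both weeks: a drug that keeps subjects awake in the trials could lower the episode count at Visit 3 by up to 4. The same drug lengthens latency. A rise from 10 to 20 minutes adds 4 × 10 = 40 still minutes (40/5,040 = 0.8 percentage points), which masks a benefit on sedentary time.

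**Subjects.** With both subsets at 50% of 230, the overlap is at most 115, 230 × 0.25 = 57.5 if the subsets are independent, and 0 if they are disjoint. The documents do not say which. The lower limit rises if more than half have the MWT, which footnote 11 allows.

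**The case against.** The best case against acting is that the text on the second week points away from an overlap. Protocol 8.4.1.15.9 and 8.4.2 both stress that wear comes before the last dose, dosing is in the morning, and 8.4.1.15.1 has subjects take the study drug before they reach the site. On that reading wear ends before the Visit 3 trials and no drug effect on the MWT enters the record. A baseline-only artefact precedes randomisation, so it cannot create a difference between arms. The amounts are small, fall on a subset of a subset, and concern a mainly exploratory outcome.

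Most of this stands. A reader might infer that an MWT drug effect will reappear as a free-living effect versus placebo. The documents do not support that as a general statement: it needs the MWT day inside the second record, and it could apply only to sleep episodes, since the sign reverses for sedentary time. Even for episodes the direction is uncertain, because SAP 10.3 detects sleep from the wearable, which may score a subject sitting awake and still as asleep.

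A reader might also infer that the polysomnography night is a main source of error. SAP 10.3 uses daytime records, so that night lies largely outside them, although the clock limits are not given.

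The objection does not dispose of the baseline overlap, which is fixed by the schedule, or of the paired pre/post tests, which have no placebo comparison to cancel a shift common to all arms.

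**Conclusion.** The point holds as a minor one. For subjects who do both assessments, the baseline week always contains the MWT day. The second week may or may not, because the wear wording, the Day 35 to 42 label and the Visit 3 window do not agree. No analysis rule removes the laboratory day.

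The size is at most 160 still minutes (3.2% of the week's daytime minutes) or at most 4 sleep episodes (about 6 minutes) per record, in 0 to 115 of 230 subjects. Episode and bout counts are more exposed than total minutes. The within-arm paired tests can be biased. Comparisons between arms are at risk only if the second record also holds the MWT day.

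This rests on three assumptions: the device stays on at the sleep centre, the manual gives no contrary rule, and the trials add stillness or sleep beyond the ordinary daytime hours they replace. The minutes are gross amounts. The net shift is smaller for a subject who would have been sitting or dozing anyway.

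**What to change.** In SAP 10.3, exclude the daytime record of the MWT calendar day from both weeks, with any other daytime hours spent at the sleep centre, and analyse bouts and sleep episodes per remaining free-living day. Protocol 8.4.1.15.7 already has trial start and stop times recorded, so the day can be identified.

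In Protocol 8.4.1.15.9, reconcile the two descriptions of the second wear window with each other and with the Visit 3 window, and state that laboratory days do not count as free-living days.

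The cost is wording in both documents and about 1 of 7 days in subjects who do both: 72 of 84 daytime hours remain, 14.3% fewer. No new data are needed.
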